d=dust mites (house), e=epidermal, f=food, g=grass, i=insect, m=mold, t=tree, w=weed

*Any profile component listed can be ordered individually. The CPT codes provided are based on AMA guidelines and are for informational purposes only. CPT coding is the sole responsibility of the billing party. Please direct any questions regarding coding to the payor being billed.

Figure 6. ImmunoCAP Allergy Profiles for IL

ImmunoCAP® Allergy Profile

Region VIII: IA, IL, MO

[figure not shown]
CHILDHOOD ALLERGY (FOOD/ENVIRONMENTAL) PROFILE

TEST CODE: 10659

SPECIMEN REQUIREMENTS: 2 mL serum, room temperature

CPT CODES*: 86003 x 15 Specific IgE; 82785 Total IgE

- *Alternaria alternata*, m6
- Cat dander, e1
- *Cladosporium herbarum*, m2
- Cockroach, i6
- Cod fish, f3
- *D. farinae*, d2
- *D. pteronyssinus*, d1
- Dog dander, e5
- Egg white, f1
- Milk, f2
- Peanut, f13
- Shrimp, f24
- Soybean, f14
- Walnut, f256
- Wheat, f4
- Total IgE

ALLERGENS INDICATED BY CAP CODES

d=dust mites (house), e=epidermal, f=food, g=grass, i=insect, m=mold, t=tree, w=weed

For additional information

- Contact client services for access to medical experts at 1 [contact]
- Contact your local sales representative for printed patient literature or visit our online patient health library at www.QuestDiagnostics.com/patienthealthlibrary

Quest, Quest Diagnostics, the associated logo, Nichols Institute, and all associated Quest Diagnostics marks are the trademarks of Quest Diagnostics.

All third-party marks — ® and ™ — are the property of their respective owners.

© 2008 Quest Diagnostics Incorporated. All rights reserved.
www.QuestDiagnostics.com MI2346-IL 03/2008

Figure 7. ImmunoCAP Allergy Profiles, **Study Timeline (Intervention):**

| Tasks | Year 1 | | | | | | | | | | | | |
|--|--------|------|-----|-----|-----|-----|-----|-----|-----|-----|-----|-----|-----|
| | Aug | Sept | Oct | Nov | Dec | Jan | Feb | Mar | Apr | May | Jun | Jul | Aug |
| Preparation Phase | | | | | | | | | | | | | |
| Web Portal | X | X | | | | | | | | | | | |
| Pilot Phase | | | X | X | X | X | X | X | X | X | X | X | x |
| Adapt Protocol | | | X | X | | | | | | | | | |
| Study Phase | | | | | | | | | | | | | |
| Recruitment | | | | | | X | X | X | X | X | X | X | X |
| Baseline Surveys | | | | | | X | X | X | X | X | X | X | X |
| Remote Health Management Device Distribution | | | | | | X | X | X | X | X | X | X | X |
| Weekly Calls/Emails to Clinic | x | X | X | X | X | X | X | X | X | X | X | X | X |
| Retention Phase | | | | | | | | | | | | | |
| 1 month surveys | | | | | | | X | X | X | x | X | X | X |
| 3 month surveys | | | | | | | | | x | x | X | X | X |
| Half-Yearly Surveys | | | | | | | | | | | | X | X |
| 9 month surveys | | | | | | | | | | | | | |
| Phone/email Follow-up | | | | | X | X | X | X | X | | | | |
| Epic Data Pull | | X | X | X | X | X | X | X | X | X | X | X | X |

| Tasks | Year 2 | | | | | | | | | | | | |
|------------------------|--------|-----|-----|-----|-----|-----|-----|-----|-----|-----|-----|-----|---|
| | Sept | Oct | Nov | Dec | Jan | Feb | Mar | Apr | May | Jun | Jul | Aug | |
| Retention Phase | | | | | | | | | | | | | |
| 9 month surveys | x | x | x | X | X | X | X | X | X | X | X | X | X |

| | | | | | | | | | | | | | |
|------------------------------------|---|---|---|---|---|---|---|---|---|---|---|---|---|
| End of the Study Surveys | x | X | X | X | X | X | X | X | X | X | X | X | X |
| Remote Health Management Data Pull | X | X | X | X | X | X | X | X | X | X | X | X | X |
| Web Portal Data Pull | X | X | X | X | X | X | X | X | X | X | X | X | X |
| Feasibility Assessment | | X | X | X | X | X | X | | | | | | |
| Analysis Phase | | | | | | | | | | | | | |
| Data Analysis | | X | X | X | X | X | X | X | X | X | x | | |
| Publications and Presentations | | | | X | X | X | X | X | X | X | X | X | X |

Study Timeline (Control):

| Tasks | Year 1 | | | | | | | | | | | | |
|--|--------|------|-----|-----|-----|-----|-----|-----|-----|-----|-----|-----|-----|
| | Aug | Sept | Oct | Nov | Dec | Jan | Feb | Mar | Apr | May | Jun | Jul | Aug |
| Preparation Phase | | | | | | | | | | | | | |
| Web Portal | X | X | | | | | | | | | | | |
| Pilot Phase | | | X | X | X | X | X | X | X | X | X | X | x |
| Adapt Protocol | | | X | X | | | | | | | | | |
| Study Phase | | | | | | | | | | | | | |
| Recruitment | | | | | | X | X | X | X | X | X | X | X |
| Baseline Surveys | | | | | | X | X | X | X | X | X | X | X |
| Remote Health Management Device Distribution | | | | | | X | X | X | X | X | X | X | X |
| Weekly Calls/Emails to Clinic | x | X | X | X | X | X | X | X | X | X | X | X | X |
| Retention Phase | | | | | | | | | | | | | |
| 1 month surveys | | | | | | | X | X | X | x | X | X | X |
| 3 month surveys | | | | | | | | | x | x | X | X | X |

| | | | | | | | | | | | | | |
|-----------------------|--|---|---|---|---|---|---|---|---|---|---|---|---|
| Half-Yearly Surveys | | | | | | | | | | | | X | X |
| 9 month surveys | | | | | | | | | | | | | |
| Phone/email Follow-up | | | | | X | X | X | X | X | | | | |
| Epic Data Pull | | X | X | X | X | X | X | X | X | X | X | X | X |

| Tasks | Year 2 | | | | | | | | | | | | |
|------------------------------------|--------|-----|-----|-----|-----|-----|-----|-----|-----|-----|-----|-----|---|
| | Sept | Oct | Nov | Dec | Jan | Feb | Mar | Apr | May | Jun | Jul | Aug | |
| Retention Phase | | | | | | | | | | | | | |
| 9 month surveys | x | x | x | X | X | X | X | X | X | X | X | X | X |
| End of the Study Surveys | x | X | X | X | X | X | X | X | X | X | X | X | X |
| Remote Health Management Data Pull | X | X | X | X | X | X | X | X | X | X | X | X | X |
| Web Portal Data Pull | X | X | X | X | X | X | X | X | X | X | X | X | X |
| Feasibility Assessment | | X | X | X | X | X | X | | | | | | |
| Analysis Phase | | | | | | | | | | | | | |
| Data Analysis | | X | X | X | X | X | X | X | X | X | x | | |
| Publications and Presentations | | | | X | X | X | X | X | X | X | X | X | X |

Clinical Outcomes

| Source | Outcome | Time Point |
|--------------------------------------|--|------------------------|
| Remote Health Management Application | ICS and SABA use | Monthly download |
| Web Portal/Epic | Asthma-related ED visits, hospitalizations, and oral corticosteroid prescriptions/courses | Monthly Epic data pull |
| Web Portal/Epic | Patient demographics pulled | Baseline |
| Parent report (Survey) | Patient age, family income, race, family makeup (single parent, two-parent household, etc) | Baseline |

| | | |
|---|--|---|
| Asthma Control Test (ACT) (ages 12 and older Or Childhood Asthma Control Test (ages 4-11) | Parent report of their child's asthma control | 5 times in total (baseline, 3 months, 6 months, 9 months, study completion) |
| Parent-reported Values (un-validated) | Asthma-related oral corticosteroid prescription/use/courses; number of asthma-related hospitalizations; number of asthma-related ED visits | 5 times in total (baseline, 3 months, 6 months, 9 months, study completion) |
| ImmunoCAP Allergen Testing | Environmental Allergens | Baseline |

Psychosocial Outcomes

| Source | Outcome | Time Point |
|---|---|---|
| Parental Asthma Management Self-Efficacy (PAMSE) | Parental self-efficacy survey to assess parent's ability to manage and/or prevent acute exacerbations | 5 times in total (baseline, 3 months, 6 months, 9 months, study completion) |
| Parent-reported values (un-validated) | School days missed due to asthma | 5 times in total (baseline, 3 months, 6 months, 9 months, study completion) |
| Pediatric Caregiver Asthma-related Quality of Life Questionnaire (PACQLQ) | Parent form of how their child's asthma is affecting both their lives and the life of their child | 5 times in total (baseline, 3 months, 6 months, 9 months, study completion) |

Parental Management Outcomes

| Source | Outcome | Time Point |
|-----------------------------------|--|---|
| Parent report (Survey) | Feasibility and acceptability of Platform | 5 times in total (baseline, 3 months, 6 months, 9 months, study completion) |
| Remote Health Management Platform | Frequency of use of the application (synching) | Monthly data pull |

Physician and Clinical Team Outcomes

| Source | Outcome | Time Point |
|-----------------------------------|---|---|
| Remote Health Management Platform | ICS and SABA use | Monthly download |
| Web Portal/Epic | Asthma-related ED visits, hospitalizations, and oral corticosteroid prescriptions/courses | Monthly Epic data pull |
| Clinician Survey | Feasibility and acceptability of the Platform | 1 month into the study, 6 months and study completion |
| Physician Survey | Feasibility and acceptability of the Platform | 1 month and study completion |
| Remote Health Management Platform | Frequency of use of the web portal | Monthly data pull |

Data Analysis:

Primary Outcomes

- *ACT*: Parent-reported test on their child's asthma control
- *Asthma-related hospitalizations*: Data will be obtained from the EMR and parent report.
- *Asthma-related ED visits*: Data will be obtained from the EMR and parent report.
- *Asthma-related oral corticosteroid use*: Prescription/course data will be obtained from the EMR and parent report.

Secondary Outcomes

- *Inhaler Use*: Use data, including frequency of both SABA and ICS inhalers, will be obtained via the sensor throughout the study period.
- *PAMSE*: Parental Asthma Management Self-Efficacy; self-report survey that measures parental self-efficacy for the management and prevention of acute exacerbations of asthma.
- *PACQLQ*: Paediatric Asthma Caregiver's Quality of Life Questionnaire; will assess the impact of their child's asthma on their lives, the lives of their children with asthma, and the family as a whole.
- *Clinical management*: To compare clinical management, data on physician-patient communication and rates of follow up will be obtained from the web portal for all patients for a year for each intervention participant. This will be measured via the number of tasks have been completed. Additionally, in the Intervention group, we will work with physicians to conduct rapid-cycle improvements to the web portal interfaces, through conversations the RA and the PI have with clinicians. We will also follow up with healthcare team to ensure follow-up calls are occurring. Finally, a four-question survey of members of the healthcare team about the acceptability and feasibility of the sensor will be conducted periodically.

Statistical Analysis:

Demographic and baseline characteristics:

Demographic and baseline characteristics including gender, age, race, ethnicity, and co-morbidities will be summarized for each treatment group and overall. The demographic and baseline characteristics summary will be based on all randomized subjects.

Baseline values for efficacy parameters (*ACT*, quality of life score, *PAMSE*) will also be presented for each treatment group and overall based on all randomized subjects.

For continuous variables, non-missing will be used to calculate the mean, median, SD, IQR, minimum and maximum by treatment group and overall. For categorical variables, the count and percentages of each possible value will be tabulated by treatment group and overall.

All comparisons of baseline characteristics between treatment groups will be adjusted for potential household clustering using robust standard errors. For continuous variables, comparability of treatment groups will be assessed using general linear models. For discrete variables, comparability will be assessed using the Cochran-Mantel-Haenszel general association test. P-values will be displayed as descriptive statistics of comparability in order to identify potential baseline imbalances with an alpha level of 0.05.

AIM 1. Determine factors influencing clinical and psychosocial outcomes.

Clinical and psychological outcomes of interest include the 12-month rate of asthma-related oral corticosteroid use, ED visits, and hospitalizations, as well as change in mean ACT scores (range of 0 to 27) from baseline to end line (12 months). Psychological outcomes of interest include quality of life score (range of 1 to 7), parental self-efficacy score, and the number of school days missed due to asthma. Potential predictors of outcomes include age (4 to 7 years vs. 8 to 17 years), gender (M vs. F), race/ethnicity (non-Hispanic white, non-Hispanic Black, Hispanic, vs. others), insurance status (private/public), and co-morbidities.

Each count variable (asthma-related oral corticosteroid use, ED visits, and hospitalizations) will be analyzed by mixed negative binomial regression analysis adjusting for treatment, all potential predictors, and including maximal random effect structures (i.e., slope and intercept as allowed by the model) of family and clinic. VIFs (variance inflation factors) will be computed for each predictor. Highly correlated predictors (i.e. predictors that can be well-explained by other predictors) will be dropped from the model to avoid multicollinearity issues. Model fit criteria, parameter estimates, and precision of parameter estimates will all be evaluated to select the most parsimonious model.

For each continuous primary outcome variable (i.e., ACT score), change-from-baseline score at each visit will be analyzed using mixed linear regression models, adjusting for treatment, time point, baseline score, all potential predictors, and including random effects (i.e., both slope and intercept) of family and clinic. A treatment by time interaction will be included to evaluate whether the effect of the treatment on the primary outcome varies by time point. VIFs will be investigated for each predictor, and those with high VIFs ($VIF \geq 10$) will be dropped from the model to avoid multicollinearity issues. An unstructured covariance (UN) matrix will be assumed. Model fit criteria, parameter estimates, and precision of parameter estimates will also be used to select the most parsimonious model.

Model diagnostics will be performed to check model assumptions. All analyses will be performed using statistical analytic software Stata Version 15.1.

AIM 2. Enhance parental management through improved inhaler use.

After the patient's enrollment visit, parents will be contacted via email or phone at 1, 3, 6, 9, and 12 months to complete a REDCap survey. Each quantitative survey item will be summarized using descriptive statistics such as frequencies and percentages along with any corresponding measures of spread. Qualitative data will be coded and analyzed by theme analysis.

The following questions will be asked:

Quantitative Questions:

1. How often do you check the sensor system?
 - More than once a daily
 - Daily
 - Once a week
 - More than once a week
 - Every other week
 - I don't check the Propeller Sensor (*If selected, participants will only answer question 1 and 5*)
2. How often in the past week did you receive useful asthma information through the sensor system?

- Once
 - Twice
 - Three or more times
 - I did not receive useful asthma information through the sensor system
3. How helpful is the sensor system in managing your child's asthma?
- Extremely helpful
 - Very helpful
 - Helpful
 - A little helpful
 - Not helpful
 - I have not checked the sensor system
4. What do you enjoy most about the sensor system?
- Easy to use
 - Ability to track inhaler use
 - Asthma Education cards
 - Other: *fill in the blank*
 - Nothing
5. Do you have any issues regarding the sensor system?
- *Comment Box*

AIM 3. Improve management by physician and clinical team.

On a biweekly basis, we will collect quantitative data from clinics on the number of time physicians' follow-up with patients and the follow-up outcome. The research team will know exactly how many alerts physicians are receiving, and how physicians are following-up with patients from the Propeller dashboard. The data from the Propeller dashboard will be summarized with descriptive statistics. Clinicians will also be contacted at 1, 3, 6, 9, and 12 months through REDCap surveys to determine if the data is helping them with management and aspects of the platform they like and dislike. Qualitative data will be coded and analyzed by theme analysis.

The following questions will be asked:

Quantitative Questions:

1. In the past week, how many times did you check the propeller dashboard?
 - Once time
 - Twice
 - 3 or more times
 - Zero
2. Are the Propeller Dashboard flags useful to you?
 - Yes
 - No
3. In the past week, how many times did you have to follow-up with patients due to alerts you received regarding the over use of Albuterol?
 - Once
 - Twice
 - 3 or more times
 - Zero
4. In the past week, how many alerts did you receive due to patients overusing albuterol?
 - One
 - Two

- 3 or more
- 5. In the past week, how many times did you have to follow-up with patients regarding their underuse of their controller medication?
 - Once
 - Twice
 - 3 or more times
- 6. In the past week, how many alerts did receive due to patients underusing their controller medication?
 - One
 - Two
 - 3 or more
 - Zero
- 7. On a scale of 1-5 (1 being the least helpful, and 5 being the most helpful), how helpful do you feel calls to patients improve asthma management?
 - 1
 - 2
 - 3
 - 4
 - 5
- 8. On a scale of 1-5 (1 being the least useful, and 5 being the most useful) how much do you think the parents found your call useful?
 - 1
 - 2
 - 3
 - 4
 - 5

Qualitative Questions:

1. What do you find useful about the Propeller dashboard?
2. What changes do you think are needed to improve the Propeller dashboard?
3. How are you currently using the Propeller dashboard? Please describe.
4. Would you utilize the Propeller health management platform for your current practice in the future?

Sample Size Determination:

Assuming asthma exacerbation rate of 0.545 for the intervention arm, and asthma exacerbation rate of 0.75 for the standard treatment arm, resulting odds ratio (OR) equal to 0.3992674, and $\log(\text{OR}) = -0.9181239$. Assuming 20% patient drop-out rate, two-sided significance level $\alpha = 0.05$, a total of 250 patients (125 per arm) is needed in order to achieve a statistical power of 85%. The sample size calculation was computed using SAS procedure PROC SEQDESIGN.

Qualitative Analyses of Semi-Structured Interviews:

Data will be analyzed systematically using a constant comparative approach; and four analysts (i.e., coders), including [name] (qualitative methods expert), [name], and 2 research team members, will meet to discuss initial thoughts, insights, and observations for the development of initial coding categories (e.g., themes). Through a systematic analysis process, themes will be continually refined by collapsing redundant themes and removing irrelevant themes. Once no new categories have emerged, a

codebook will be developed for the remaining analysis. We will construct a saturation grid, to track themes as they emerge and determine when no new information is obtained

Study Staff:

[name] will oversee study operation at participating sites and will be responsible for the acquisition and handling of study data according to the procedures outlined in this protocol. The research team will be comprised of a research manager, research assistants, research coordinators, a data analyst, and a biostatistician. A member of the research team, along with Propeller Health will be responsible for the web portal integration of sensor data in the web portal. A Lurie Children's Epic personnel will be responsible for extracting EMR data. United Health Care Group will be involved or consulted in every aspect of the study.

Data Privacy and Human Subject Consideration:

Direct benefit:

Remote Health Management Group (Intervention): Children will have use of an inhaler sensor that may improve asthma management by tracking ICS and SABA use. The sensor software also sends tailored education materials to caregivers and alerts primary care physicians of increased SABA use. This enhanced care may lead to fewer asthma exacerbations, resulting in fewer school and/or work days missed, fewer ED visits, and fewer hospitalizations.

Standardized Education Group: Children in this group will have standardized education (proper inhaler technique and a visual action plan), which may lead to better asthma outcomes as well.

Indirect benefit: Eventual development of an insurance-wide program for children to better manage their asthma.

Risks: The primary risk to participants in this study is discomfort related to getting blood drawn for the ImmunoCAP allergen testing. We will teach participating families to properly use all applications before the intervention begins. There is also a risk of confidentiality.

To protect personal health information (PHI), each child will be given a study ID number, which will be kept separate from sensor and questionnaire data on a secure, password-protected database at Northwestern University. All sensor data will be securely downloaded from the cloud by the Remote Health Management provider, and sent securely to Northwestern to store on secure servers. All EMR data will be de-identified and saved in the same manner.

Patient Safety Monitoring Plan:

The patient safety monitoring plan for this study will include:

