# AIM 1. Determine factors influencing clinical and psychosocial outcomes.

Clinical and psychological outcomes of interest include the 12-month rate of asthma-related oral corticosteroid use, ED visits, and hospitalizations, as well as change in mean ACT scores (range of 0 to 27) from baseline to end line (12 months). Psychological outcomes of interest include quality of life score (range of 1 to 7), parental self-efficacy score, and the number of school days missed due to asthma. Potential predictors of outcomes include age (4 to 7 years vs. 8 to 17 years), gender (M vs. F), race/ethnicity (non-Hispanic white, non-Hispanic Black, Hispanic, vs. others), insurance status (private/public), and co-morbidities.

Each count variable (asthma-related oral corticosteroid use, ED visits, and hospitalizations) will be analyzed by mixed negative binomial regression analysis adjusting for treatment, all potential predictors, and including maximal random effect structures (i.e., slope and intercept as allowed by the model) of family and clinic. VIFs (variance inflation factors) will be computed for each predictor. Highly correlated predictors (i.e. predictors that can be well-explained by other predictors) will be dropped from the model to avoid multicollinearity issues. Model fit criteria, parameter estimates, and precision of parameter estimates will all be evaluated to select the most parsimonious model.

For each continuous primary outcome variable (i.e., ACT score), change-from-baseline score at each visit will be analyzed using mixed linear regression models, adjusting for treatment, time point, baseline score, all potential predictors, and including random effects (i.e., both slope and intercept) of family and clinic. A treatment by time interaction will be included to evaluate whether the effect of the treatment on the primary outcome varies by time point. VIFs will be investigated for each predictor, and those with high VIFs (VIF>=10) will be dropped from the model to avoid multicollinearity issues. An unstructured covariance (UN) matrix will be assumed. Model fit criteria, parameter estimates, and precision of parameter estimates will also be used to select the most parsimonious model. Model diagnostics will be performed to check model assumptions. All analyses will be performed using statistical analytic software Stata Version 15.1.

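### The ACT model uses one baseline slope for all visits; if the correlation with baseline falls over follow-up, the 12-month comparison can lose a little precision, and a baseline-by-time term avoids this

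*Protocol*

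**What the plan says.** The protocol (Statistical Analysis, AIM 1) and the SAP (AIM 1) carry the same model text for ACT. The outcome and fixed effects are: "change-from-baseline score at each visit will be analyzed using mixed linear regression models, adjusting for treatment, time point, baseline score, all potential predictors". One interaction is named: "A treatment by time interaction will be included to evaluate whether the effect of the treatment on the primary outcome varies by time point". The model is described as "including random effects (i.e., both slope and intercept) of family and clinic", and then: "An unstructured covariance (UN) matrix will be assumed". Neither document says whether that matrix belongs to the within-child residuals or to the random effects, or whether time point is categorical. The listed candidate predictors are demographic and clinical, and no baseline-by-time term is among them. The model may then be reduced: "Model fit criteria, parameter estimates, and precision of parameter estimates will also be used to select the most parsimonious model".

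The time point of interest for ACT is given as "change in mean ACT scores (range of 0 to 27) from baseline to end line (12 months").

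The ACT schedule is not consistent. Sections 8 to 12 of Study Design and Procedures have caregivers complete the ACT at 1, 3, 6, 9 and 12 months, and AIM 2 of the protocol says "parents will be contacted via email or phone at 1, 3, 6, 9, and 12 months to complete a REDCap survey". The Clinical Outcomes table lists ACT at baseline, 3, 6 and 9 months and study completion, with no month 1. The Timeline at the end of the protocol counts five survey rounds.

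**The concern.** The treatment effect may differ at each visit, but the baseline coefficient may not. If baseline symptom control predicts the month-1 score better than the month-12 score, no single slope suits both. The fitted slope is then a compromise, too steep at month 12, and the chance baseline difference between the arms is over-corrected there.

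What is at stake is the precision of the month-12 ACT contrast, one of four listed primary outcomes. Some decay is plausible here. Every child has had a steroid-treated exacerbation in the past year, and some may be recruited as inpatients after an exacerbation, so their baseline may reflect an acute state. That is an inference from the eligibility and enrolment text, not something the documents report.

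**Working it through.** **The plan's own figure.** The only power calculation is for the exacerbation rate: 0.545 against 0.75, log odds ratio -0.9181, two-sided 5%, power 85%, 20% drop-out. A Wald calculation on the log odds ratio gives, per arm,

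(1.960 + 1.036)² × [1/(0.545 × 0.455) + 1/(0.75 × 0.25)] / 0.9181² = 99.8, rounded to 100.

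100/0.8 = 125 per arm, 250 in total, as stated. This says nothing about ACT, but it supplies a working number of 200 completers.

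**Assumptions, none of them in the documents.** Equal ACT SDs at all visits (set to 1), complete data, categorical time, an unstructured within-child residual covariance, and the correlation patterns in the table.

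**Formulas.** Let r be the vector of correlations of each follow-up visit with baseline, r12 its month-12 element, and S0 the covariance of the follow-up visits given baseline.

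- Common slope: b = (1'S0⁻¹r)/(1'S0⁻¹1).
- Best month-12 slope: r12. Modelling change instead of final score subtracts 1 from both slopes, so the gap is the same.
- Month-12 effect: difference in mean change, less the fitted slope times the baseline difference. Relative to visit-specific slopes its variance is multiplied by 1 + (b - r12)²/(1 - r12²).

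**Worked case.** The correlation between visits m months apart is 0.8 × 0.9^m. With baseline it is 0.720, 0.583, 0.425, 0.310 and 0.226 at months 1, 3, 6, 9 and 12. The common slope is b = 0.549. The ratio is 1 + (0.549 - 0.226)²/(1 - 0.226²) = 1 + 0.104/0.949 = 1.110. The SE rises by 5.4%, since √1.110 = 1.054, and 200 completers act like 200/1.110 = 180.

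| Correlation at lag m months | Month 1 | Month 12 | b (visits 1/3/6/9/12) | Variance, visits 1/3/6/9/12 | Variance, visits 3/6/9/12 |
|---|---|---|---|---|---|
| constant 0.5 | 0.500 | 0.500 | 0.500 | 0 | 0 |
| 0.4 + 0.2e^(-m/4) | 0.556 | 0.410 | 0.476 | +0.5% | +0.2% |
| 0.3 + 0.4e^(-m/4) | 0.612 | 0.320 | 0.467 | +2.4% | +0.7% |
| 0.2 + 0.5e^(-m/4) | 0.589 | 0.225 | 0.407 | +3.5% | +1.0% |
| 0.3 + 0.5e^(-m/4) | 0.689 | 0.325 | 0.528 | +4.6% | +1.2% |
| 0.1 + 0.7e^(-m/4) | 0.645 | 0.135 | 0.405 | +7.5% | +1.9% |
| 0.8 × 0.9^m | 0.720 | 0.226 | 0.549 | +11.0% | +4.6% |

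The table is a selection. Across a wider set of moderate to strong decay patterns the ranges were about 1.5 to 11% with a month-1 visit and about 0.4 to 4.6% without. The mildest row falls below both.

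**Where the slope comes from.** With five visits, month 1 carries 20% of the weight under constant correlation, 28 to 42% in the decay-to-a-floor rows and 47% in the last row. Month 12 carries 17 to 19% in the decaying rows.

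**An extreme for reference.** Pure first-order autoregression with no visit-to-visit noise (month-12 correlation 0.2 to 0.5) raises the SE by 10.8 to 14.5% with a month-1 visit and by 4.7 to 5.3% without. It implies a correlation of 0.87 to 0.94 over one month, so it is a limit rather than a working case.

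**Simulation.** In 6,000 simulated trials of 100 per arm with month 1 included, the SE rose by 0.8% for 0.3 + 0.4e^(-m/4) (formula 1.2%) and by 3.4% for 0.1 + 0.7e^(-m/4) (formula 3.7%). Mean effects were within 0.002 SD of the true value of zero under both models, so neither showed bias.

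**The case against.** The strongest reply is that this is not an error. Adjusting with one baseline slope is a standard model, randomisation protects the month-12 contrast, and no stated figure is wrong. All of that stands.

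A reader might infer more: that the common slope is in fact fitted mainly to the early visits, and that the month-12 effect does lose precision. The documents do not support this, because they report no ACT correlations. Under constant correlation every visit has equal weight and nothing is lost. The pull towards early visits also depends on what the unstructured matrix applies to. If visits were weighted equally, b would be the mean of the visit slopes. In the last table row that is (0.720 + 0.583 + 0.425 + 0.310 + 0.226)/5 = 0.453, and the inflation falls from 11.0% to 0.227²/0.949 = 5.4%. The larger figures also need a month-1 ACT, which the Clinical Outcomes table omits.

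A reader might also infer that the value of measuring baseline ACT is lost at month 12. In the last row the residual variance is 1 - 2(0.549)(0.226) + 0.549² = 1.05 times the unadjusted final-score variance, so the planned adjustment is slightly worse than none. But this needs a month-12 correlation near 0.2 together with strong decay. Even the right slope would then remove only 0.226² = 5% of the variance, so little was there to lose.

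The promised model diagnostics could reveal a changing baseline slope. They do not commit the team to adding the term, and the parsimony rule works in the other direction.

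**Conclusion.** The point holds as a minor, conditional one. Both documents give baseline ACT a single slope while the ACT outcome is the 12-month change. If correlation with baseline decays, the month-12 variance rises by about 1.5 to 11% with visits at 1, 3, 6, 9 and 12 months and by about 0.4 to 5% with visits at 3, 6, 9 and 12 months. It rises less under mild decay and not at all under constant correlation. At the top of the range, a comparison assumed to have 80% power would have about 76%: (1.960 + 0.842)/1.054 - 1.960 = 0.70. The documents state no power for ACT, so the 80% is illustrative.

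The size rests on assumed correlations, equal SDs, categorical time and an unstructured within-child residual covariance. The concern is precision, not bias; drop-out related to baseline was not examined.

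**What to change.** In AIM 1 of the protocol and of the SAP, add a baseline-ACT-by-time-point interaction to the ACT model beside treatment by time. State that neither interaction is subject to the parsimony selection; otherwise the added term could be dropped again. In the same edit, say that time point is categorical, say which covariance is unstructured, and settle whether the month-1 ACT enters the model.

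The cost is one or two sentences and four extra parameters with five follow-up visits, or three with four. No new data are needed, and essentially nothing is lost if the correlations turn out constant. The term should be fixed before any treatment comparison is seen, since adding it later would be a data-driven change to a primary analysis.
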